ASR	Annual Safety Report = the annual safety report for reporting to authorities. In Sweden this is the Swedish Medical Products Agency via CTIS
Bd	Bis Die (twice daily)
CBCT Voltage	Cone Beam Computed Tomography voltage. The voltage used in CBCT is usually in the range of 120-140 kV.
CRP	C-Reactive Protein
CRT	Chemoradiotherapy
cCR	clinical Complete Response
CRF	Case Report Form
CT	Computerized Tomography
CTIS	Clinical Trials Information System = Centralized EU database/portal for application and communication with authorities concerning clinical trials. In Sweden this includes the Swedish Medical Products Agency and the Swedish Ethical Review Authority.
CTR	EU Regulation 536/2014, also called CTR, Clinical Trials Regulation
CTCAE	Common Terminology Criteria for Adverse Events
ctDNA	circulating tumour Deoxyribonucleic Acid
DPYD	Dihydropyrimidine Dehydrogenase
DSUR	Development Safety Update Report = the standard which should be used for annual safety reporting to authorities
EMVI	Extramural Vascular Invasion
EORTC	European Organization for Research and Treatment of Cancer
FFPE	Formalin Fixed Paraffin-embedded
GCP	Good Clinical Practice
GFR	Glomerular Filtration Rate
Gy	Grey, the unit of ionizing radiation dose in the International System of Units (SI), defined as the absorption of one joule of radiation
H&E	Haematoxylin and Eosin
HRQoL	Health-Related Quality of Life
IB	Investigator's Brochure
ITT	Intention-to-treat = including all data from all subjects who have participated in the trial
LARS	Low Anterior Resection Syndrome
Läkemedelsverket	Swedish Medical Products Agency – the national authority responsible for regulation and surveillance of the development, manufacturing and sale of medicinal products

Member State	European Union (EU) Member state where an application for authorisation of a clinical trial or of a substantial modification has been submitted.
MDT	Multidisciplinary Team
MRI	Magnetic Resonance Imaging
OAR	Organs at Risk
PP	Per Protocol analysis = including only data from subjects who have completed the trial completely in accordance with the protocol, with no deviations from the protocol
QoL	Quality of life (here often health related quality of life, but not excluding global quality of life)
RSI	Reference safety information. A list of all known serious adverse reactions for the investigational medicinal product, including severity and frequency of the adverse reaction. The RSI is contained in the Summary of Product Characteristics or IB and is used to determine which adverse reactions should be reported as suspected unexpected serious adverse reactions (SUSARs).
SAE	Serious Adverse Event: Any untoward medical occurrence that at any dose requires inpatient hospitalisation or prolongation of existing hospitalisation, results in persistent or significant disability or incapacity, results in a congenital anomaly or birth defect, is life-threatening, or results in death
SAR	Serious Adverse Reaction
SCRCR	Swedish ColoRectal Cancer Registry
SP or SmPC	Summary of Product Characteristics
SUSAR	Suspected Unexpected Serious Adverse Reaction: This is an event that is likely related to the investigational medicinal product but with unexpected occurrence. An adverse reaction is unexpected if its nature or seriousness is not consistent with the information on the product in the RSI.
T1	Tumour invading the submucosa
T2	Tumour invading the muscularis propria
T3	Tumour invades into subserosa or into non-peritonealised pericolic or perirectal tissues
T4	Tumour perforates visceral peritoneum (4a) and/or directly invades other organs or structures (4b)
TEM	Transanal Endoscopic Microsurgery
TME	Total Mesorectal Excision
ULN	Upper Limit of Normal

165

166

167

168 1.0 SYNOPSIS

EU Trial number:	2025-522955-25-00
Title:	Next generation StaR-TREC -Save the rectum by watchful waiting after (chemo)Radiotherapy or Total mesorectal excision for early REctal Cancer?
Trial ID:	NG-ST
Short background/ Rationale/Aim:	
In patients with a newly diagnosed early rectal cancer the primary treatment is surgery without previous neoadjuvant treatment. However, the surgical treatment is associated with complications and if surgery could be avoided maintaining curative intent it is possible that QoL could be improved. One way of achieving this goal is to treat patients with chemoradiotherapy prior to planned surgery. If the patient responds with a clinical complete response (cCR), leaving no visible tumour surgery could be avoided. This is often called organ preservation.
 
In the international multicentre randomized study, STAR-TREC (NCT02945566), patients were offered the choice of choose surgical treatment or possible organ preservation.
 
Those who preferred organ preservation were randomised 1:1 between (i) organ preservation with mesorectal Chemoradiotherapy (CRT) versus (ii) organ preservation with mesorectal Short Course Radiotherapy (SCRT).
 
The trial closed patient entry in end of March 2024 after having randomized the planned number of patients (in the combined phase II and III a total of 344 patients). IN the experience with the experimental treatments were that they were well tolerated by patients. Many patients were interested in the possibility to participate in the study. One year follow-up indicates that CRT renders almost 60% of patients a clinical complete response (with the addition of local excision this number was increased to 79%).
 
In light the emerging demand from patients to offer the possibility of a non-surgical option to patients with early tumours until the results from the STAR-TREC trial are available this study has been developed. Organ preservation without detailed specification is included as a possibility in the recent guidelines for treatment of colorectal cancer in Sweden.
 
In consensus in the oncologic and surgical community in Sweden mesorectal chemoradiotherapy has been suggested as a treatment option to standard rectal resection.

Primary objective:	Can mesorectal chemoradiotherapy achieve clinical complete response in early rectal cancer that is sustainable so that patients defer/avoid surgery?
Secondary objectives:	
Oncologic: Local recurrence, mortality and overall survival
 
Surgical: Complications and hospital stay
 
Patient reported outcomes: Quality of life, urinary function, sexual function, bowel and stoma function

Health economy	
Primary endpoint:	Clinical complete response rate evaluated by MRI and endoscopy at one year (i.e. patients that have not undergone surgery)
Secondary endpoint:	
 • Oncologic: 
 ○ Clinical complete response rate without surgical intervention at three years ○ Local recurrence at three years ○ Mortality at three years ○ Overall survival at three years • Surgical 
 ○ Surgical morbidity measured as Comprehensive Complications index at 90 days after surgery (if performed) ○ Total length of hospital stay during the first year ○ Outcome after surgery (Histopathological assessment of the resected rectal specimen to report (a) Presence of clear margins (>1mm from excision border to tumour edge), (b) TNM staging.) • Patient reported outcomes (all measured Baseline, post treatment, at surgery if applicable and at one, two and three years) 
 ○ Quality of life ○ Urinary function ○ Sexual function ○ Bowel and stoma function 
Health economic analysis at three years

Trial design:	
National, multi-centre, open-label, prospective trial.
 
Patients will choose possible organ preservation or standard surgery.
 
Those who prefer possible organ preservation will be offered treatment according to the experimental arm of the STAR TREC trial: mesorectal Chemoradiotherapy (CRT).
 
Those who prefer standard surgery or have no preference will undergo standard Total Mesorectal Excision (TME) surgery without neoadjuvant radiotherapy treatment.

Trial population:	Subjects referred to either a colorectal surgeon or the colorectal cancer multidisciplinary team (MDT) with suspected early stage rectal cancer (T1-T3bNx/N0). Diagnosis must be confirmed with a biopsy prior to study entry.
Number of subjects:	Due to the study design the number of patients to be included has not been fixed, but it is estimated to be at least 60-80 patients during the period until STAR-TREC data will be available
Inclusion criteria:	
 • Biopsy proven adenocarcinoma of the rectum < 12 cm • Magnetic Resonance Imaging (MRI)-staged TT1-3b, N0, MX/M0 rectal tumour • MDT determines that the following treatment options are all

	
reasonable and feasible: TME surgery or CRT
 
 • Eastern Cooperative Oncology Group (ECOG) performance status 0-1 • Willing and able to consent
Exclusion criteria:	
 • MRI node positive ($\geq N1$, defined by protocol guidelines) • MRI extramural vascular invasion (mriEMVI) present (defined by protocol guidelines) • MRI defined mucinous tumour • Mesorectal fascia threatened by tumour (≤ 1 mm on MRI or ERUS) • Maximum tumour diameter >40 mm (either measured from everted edges on sagittal MRI or ERUS examination) • No residual luminal tumour following endoscopic mucosal resection or similar local excision • Prior pelvic radiotherapy • Definite evidence of regional or distant metastases (M1) in opinion of MDT • Uncontrolled cardiorespiratory comorbidity (inadequately controlled angina or myocardial infarction or arrhythmia within 6 months prior to trial entry) • Known complete Dihydropyrimidine Dehydrogenase deficiency • Known Gilbert's disease • Medication with coumarin-derivative oral anticoagulants that cannot be stopped or substituted by low molecular weight heparin • Medication with metronidazole, phenytoin, sorivudine or its analogues, such as brivudine • Pregnancy or breast feeding • Age <18 years
Intervention:	
This is a low intervention trial as the investigational medicinal product (Capecitabine) is already authorized, used according to the terms in its marketing authorization to the same diagnosis but at a different tumour stage than standard and the complementary diagnostic procedures do not contribute to the risk or burden to subject safety compared to normal clinical practice.
 
Patients will choose organ preservation or standard surgery. Those who prefer organ preservation will be treated with mesorectal CRT
 
Those who prefer standard surgery or have no preference, will undergo standard TME surgery without neoadjuvant treatment. They will be asked to participate in the QoL part of the study, while the remainder of the data will be extracted from the national quality registry, the Swedish ColoRectal Cancer Registry (SCRCR)
 
Long course concurrent chemoradiation (CRT): Capecitabine: 825 mg/m² orally, b.d., on radiotherapy days Radiotherapy: A dose of 50 Gy applied to the primary tumour and surrounding mesorectum in 25 fractions of 2 Gy, 5 days a week.

	
The first assessment after treatment is at 6-8 weeks (from end of chemoradiotherapy) using composite clinical, endoscopic and MRI based assessment will identify the minority of non-responders who should convert to TME surgery. Patients demonstrating a clinical Complete Response (cCR) after chemoradiotherapy 6-8 weeks will be offered to enter the national watch and wait program and followed accordingly in the WoW study NCT03125343 (3, 6, 9, 12, 15, 18, 21 and 24 months and then every 6 months for another 3 years and then yearly for five more years).
 
If near complete response there will be a re-evaluation after 12 weeks after chemoradiotherapy to determine if the criteria for clinical complete response (cCR) are met.
 
Regardless of timepoint, patients who achieve CR may progress directly to active surveillance. Those who do not fulfil the criteria for CR will progress to TME-surgery.

Investigational medicinal product(s), dosage, administration:	
Capecitabine: 825 mg/m² administered orally twice daily on radiotherapy days
 
Radiotherapy: A dose of 50 Gy applied to the primary tumour and surrounding mesorectum in 25 fractions of 2 Gy, 5 days a week.

Ethical considerations, benefit/risk:	
The treatment suggested has been evaluated at one year after finalized treatment with little known severe side effects. The benefit for the patients is that the treatment is offered as it is yet to be standardized in Sweden according to national treatment guidelines. Possible risks include increased risk for complications if surgery is deemed necessary, but according to previous publications this risk is small.

Planned duration of the trial:	
About two-year inclusion, and at least three-year follow up after inclusion of the last patient.

169

170

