9.1.2 Serious Adverse Event (SAE)

A serious adverse event is any untoward medical occurrence or effect that at any dose:

- results in death
- is life threatening (at the time of the event)
- requires hospitalisation or prolongation of existing inpatients' hospitalisation
- results in persistent or significant disability or incapacity
- is a congenital anomaly or birth defect
- is a new event of the trial likely to affect the safety of the subjects, such as an unexpected outcome of an adverse reaction, lack of efficacy of an IMP used for the treatment of a life-threatening disease, major safety finding from a newly completed animal study, etc.

SAEs that result in death or are life threatening should be reported expedited. The expedited reporting will occur not later than 7 days after the responsible investigator has first knowledge of the adverse reaction. This is for a preliminary report with another 8 days for completion of the report.

All SAEs, irrespective of relationship to the study treatment must be reported to the Datacentre.

The SAE report should include the investigator's assessment of causality. If follow-up information changes the investigator's assessment of causality, this should be noted on the SAEs occurring within 30 days after discontinuation of the study treatment should be reported.

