9.1.3 Suspected Unexpected Serious Adverse Reaction (SUSAR)

Adverse reactions are all untoward and unintended responses to an investigational product

836 related to any dose administered.

837 Unexpected adverse reactions are adverse reactions, of which the nature, or severity, is not
838 consistent with the applicable product information (e.g. Investigator's Brochure for an
839 unapproved IMP or Summary of Product Characteristics (SPC) for an authorised medicinal

840 9.2 Assessment of Adverse Events (AE)

841 9.2.1 Assessment of causal relationship

842 The investigator is responsible for determining whether there is a causal relationship between
843 the AE/SAE and use of the investigational medicinal product.

844 Consideration should be given to whether there is a reasonable possibility of establishing a
845 causal relationship between the adverse event and the investigational medicinal product based
846 on the analysis of the available evidence.

847 All AE can be categorized as either likely related, possibly related, unlikely related or not
848 related, in accordance with the definitions below:

849 **Likely related:** Clinical event, including abnormal results from laboratory analyses, occurring
850 within a reasonable time after administration of the intervention/investigational medicinal
851 product. It is unlikely that the event can be attributed to underlying disease or other
852 medications but is most likely caused by the investigational medicinal product and its
853 emergence is reasonable in relationship with use of the investigational medicinal product.

854 **Possibly related:** Clinical event, including abnormal results from laboratory analyses,
855 occurring within a reasonable time after administration of the intervention/investigational
856 medicinal product. The event could be explained by the investigational medicinal product,
857 and its emergence is reasonable in relationship with use of the investigational medicinal
858 product, but there is insufficient information to determine the relationship. The event could be
859 explained by an underlying disease or other medications.

860 **Unlikely related:** Clinical event, including abnormal responses from laboratory tests, unlikely
861 to be related to the intervention/investigational medicinal product and can be reasonably
862 explained by other medication or underlying disease.

863 **Not related:** Clinical event, including abnormal results from laboratory analyses, that is not

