9.3.2. Reporting of Suspected Unexpected Serious Adverse Reactions (SUSAR)

Those SAE which are assessed by sponsor to be SUSAR are to be reported to the EudraVigilance database. The completed CIOMS form will be the basis for the reporting, by Swedish Medical Products Agency in the EudraVigilance database according to the specified time frames.

SUSAR that are fatal or life-threatening are reported as soon as possible and no later than 7 days after the SAE has become known to the sponsor. Relevant follow-up information is sent thereafter within an additional 8 days. Other SUSAR are reported as soon as possible and no later than 15 days after they have come to the sponsor's knowledge.

Information about SUSAR occurring during the trial is compiled by the sponsor and sent to the principal investigators at all participating sites.

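### The SUSAR definition requires a likely relation to the drug, but the causality scale has a separate possibly-related grade, and the protocol does not say which grades count as suspected

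*Protocol*

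**What the plan says.** The list of abbreviations gives a working definition of a SUSAR as well as spelling out the letters: "This is an event that is likely related to the investigational medicinal product but with unexpected occurrence".

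Section 9.2.1 sets the causality scale: "All AE can be categorized as either likely related, possibly related, unlikely related or not" related. *Likely related* is demanding, because other disease or medication must be an improbable explanation. For *possibly related* the text says "The event could be explained by the investigational medicinal product", while another cause remains open and the information does not settle the matter.

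The SUSAR reporting section (the second of two sections numbered 9.3.2) leaves the classification to the sponsor: "Those SAE which are assessed by sponsor to be SUSAR are to be reported to the EudraVigilance database". It sets 7 days for fatal or life-threatening SUSARs and 15 days for the others, and has the sponsor inform the principal investigators at all sites.

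Section 9.1.2 adds a rule for SAEs in general: "SAEs that result in death or are life threatening should be reported expedited".

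**The concern.** The first S in SUSAR stands for suspected. An event that the protocol itself says the drug could explain is suspected in the ordinary sense. Yet the one place that ties SUSAR status to a causality grade uses the name of the higher grade and leaves the lower one out. This is a stated rule that points the wrong way, not a detail left for another document.

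At stake are the 15-day report to the authority's database and the notice to the other investigators while patients are still being treated. Section 9.5 appoints no formal safety committee, so these notices carry more weight than they would otherwise. Attribution may also be difficult: capecitabine is the only investigational product (section 7.1) and is taken only on radiotherapy days (section 7.1.1), so it is given alongside a treatment with toxicity of its own.

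**Working it through.** No arithmetic applies. The check sets the relevant texts side by side and asks what each requires of causality.

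| Place in the protocol | What it governs | Causality condition |
|---|---|---|
| List of abbreviations, SUSAR | Definition of a SUSAR | *Likely related* |
| 9.1.3 | Adverse reactions and unexpectedness | Related to any dose; no grade named |
| 9.2.1, opening | General standard for judging causality | A reasonable possibility; no grade named |
| 9.2.1, scale | Grading of every AE | Four grades; none mapped to suspected |
| 9.2.1, end | Follow-up of AEs suspected to be caused by the drug | Suspected; not mapped to grades |
| 9.3.2 (second), SUSAR reporting | 7- and 15-day reports, notice to sites | Sponsor's assessment; no grade named |
| 9.3.2 (first), SAE reporting | Report to sponsor within 24 hours | None |
| 9.1.2 | Expedited reporting of fatal or life-threatening SAEs | No grade named |

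Step 1. The body text is wider than the list. Section 9.1.3 says "Adverse reactions are all untoward and unintended responses to an investigational product" related to a dose, and section 9.2.1 opens with "Consideration should be given to whether there is a reasonable possibility of establishing a" causal link. A reasonable possibility is a lower bar than likely. Neither text says which of the four grades meets it.

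Step 2. Take an unexpected SAE and apply the list's definition literally, using the 9.2.1 scale.

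- Rated *likely related*: a SUSAR, with all the reporting that follows.
- Rated *possibly related*, fatal or life-threatening: not a SUSAR by the list, but expedited under section 9.1.2, with a preliminary report within 7 days and 8 more days to complete it.
- Rated *possibly related*, serious for another reason such as hospitalisation or disability: not a SUSAR by the list. It reaches the sponsor within 24 hours, but neither the 15-day report nor the notice to sites is triggered.
- Rated *unlikely* or *not related*: not a SUSAR on either reading.

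Step 3. The loss of the 15-day report is therefore confined to the third case. The notice to sites also depends on SUSAR status, because section 9.1.2 names neither a recipient nor such a notice.

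Limit of the check: in the text at hand section 9.1.3 breaks off in mid-sentence, just before section 9.2. This is taken as a fault of the text extraction. The statement that no other place fixes a grade covers only the text that can be read.

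**The case against.** The best defence is that a line in a list of abbreviations is not the reporting rule. It does not refer to the 9.2.1 scale, and the operative sections never repeat *likely*. They speak of relation, reasonable possibility and suspicion, and leave the decision to the sponsor. A sponsor who follows those sections may well report possibly related events correctly. This stands, and it makes the consequence conditional. It does not remove the inconsistency: someone who needs a cut-off will find only one, and it is the narrow one.

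The defence also points to other routes that do not depend on the causality grade. All SAEs reach the sponsor within 24 hours. Unexpected events that may affect benefit and risk are notified within 15 days (section 11.4). Urgent safety measures are notified within 7 days (section 9.7), and there is an annual safety report (section 9.6). These soften the effect, but none of them is the case-by-case SUSAR report or its notice to sites. Section 9.2.1 has both views recorded when sponsor and investigator disagree on causality, but does not say whose grade decides SUSAR status.

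Two stronger readings are tempting and should not be made. A reader might infer that all possibly related unexpected serious reactions fall outside expedited reporting. Section 9.1.2 contradicts this for fatal and life-threatening events, and for the rest it follows only if the list overrides the body. A reader might also infer that most serious events will be rated *possibly related*, so that the definition removes the commoner grade. The protocol gives no figure for this, and postoperative events could equally be rated unlikely or not related to capecitabine.

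**Conclusion.** The point holds in a limited form. The definition list and the 9.2.1 scale do not agree, and no readable text resolves the difference. The exposure is mainly unexpected SAEs rated *possibly related* that are neither fatal nor life-threatening, and it arises only where the list's wording is applied. For those events the 15-day report and the notice to all principal investigators could be missed.

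The number of such events cannot be estimated, because the protocol states no expected SAE or SUSAR rate. The conclusion assumes that the unreadable end of section 9.1.3 does not assign grades. The point concerns safety reporting alone and has no bearing on the primary endpoint, sample size, alpha or analysis. It should be corrected, because the stated threshold is wrong as worded and the correction is small.

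**What to change.** Replace the *likely related* condition in the list of abbreviations, and put the same rule in section 9.1.3 and the SUSAR reporting section. Suggested sense: an SAE rated likely or possibly related to the investigational product by the investigator or by the sponsor, and unexpected against the reference safety information, is handled as a SUSAR.

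The test of unexpectedness should be aligned in the same edit, since the list refers to nature or seriousness and section 9.1.3 to nature or severity.

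The cost is about one sentence in three places and possibly a few more expedited reports. Treatment, data collection and analysis do not change.
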